2.7 ELIGIBILITY

Inclusion criteria:

- Adults (aged 16 and over)
- Registered in a participating GP practice
- Previously prescribed statin treatment in the last 3 years
- Stopped OR is considering stopping statin treatment due to muscle symptoms
- Provided fully informed consent.

Exclusion criteria:

- Any previously documented serum alanine aminotransferase (ALT) levels at or above three times the upper limit of normal
- Have persistent, generalised, unexplained muscle pain (whether associated or not with statin use) and have creatinine kinase (CK) levels greater than 5 times the upper limit of normal
- Any contraindications listed in the Summary of Product Characteristics for Atorvastatin 20 mg (Appendix 8)
- Should not participate in the trial in the opinion of the general practitioner.

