2.2 OPTIONAL GENETIC STUDY

A genetic component to statin myopathy (pain accompanied by rises in CK or ALT) has been suggested (the SLCO1B1 variant).¹⁸ However, it is not clear whether this variant will be found among the patients included in our study (who have experienced muscle symptoms while on statins but no substantial rises in CK or ALT). Therefore, as part of the trial, we will ask patients to provide a blood sample for an optional genetic analysis as part of a larger collaborative effort investigating genetic associations with statins' effects. Specific results will not be fed back to clinicians or to patients.

Where patients have consented for the genetic blood test, one nine millilitres blood sample will be obtained in an EDTA Vacutainer tube, labelled with the genetic study ID number, patient's gender, and the date and time of sample collection. It will then be sent to the genetics laboratory at the University of Liverpool via first class post in pre-paid Royal Mail Safeboxes (each containing a

maximum of four tubes) as soon as possible after collection. No patient identifiable data will be included or separately provided to the University of Liverpool.

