Appendix 2: StatinWISE Baseline data form

1. Patient Initials				2. Patient Screening ID				-				3. Site ID			
4. Visit date	dd/mm/yyyy			5. Gender											
6. Ethnicity	a. White: (i) British (ii) Irish (iii) Traveller (iv) Other b. Black: (i) African (ii) Caribbean (iii) Black British (iv) Other c. Asian: (i) Asian British (ii) Indian (iii) Pakistani (iv) Chinese (v) Other d. Mixed e. Other: (describe) _____												Circle main group and sub-group		
7. Age	 		Years												

Patient Personal Details: The following information is needed for trial management purposes (sending trial medication and reminders) only and will not be collected as part of the trial database.

A. Full name	First name		Last name			
B. Postal address	House number/Name					
	Street name					
	Town/City					
	Postcode					
C. Email (primary)			D. Email (secondary)			
E. Home Telephone			F. Mobile number			

ELIGIBILITY ASSESSMENT (Circling any RED box means patient is NOT eligible)			Eligibility Please circle	
8. Written informed consent obtained?			YES	NO*
9. Is the patient aged 16 and over?			YES	NO*
10. Patient has a clinical reason for treatment with atorvastatin 20mg daily?			YES	NO*
11. Used statin within the last 3 years?			YES	NO*
12. Is patient considering discontinuation of their statin due to muscle related adverse effects OR Has patient stopped taking a statin due to muscle related adverse effects?			YES	NO*
13. Can atorvastatin 20mg daily be started or continued in the GP's opinion?			YES	NO*
14. Has patient had previously documented ALT levels at or above three times the upper limit of normal (ULN)? Test date: dd/mm/yyyy (must be within 3 months of visit) Result:    iU/L			YES*	NO
15. Does the patient have persistent, generalised, unexplained muscle pain (whether associated or not with statin use) and have creatinine kinase (CK) levels greater than 5 times the upper limit of normal? Test date: dd/mm/yyyy (must be within 3 months of visit) Result:    U/L			YES*	NO

*if circled, patient is NOT eligible

PATIENT GENERAL MEDICAL HISTORY

16. Symptoms experienced during statin use that the patient believed were caused by the statin:

(a) Muscle pain	YES/NO	(f) Sore throat	YES/NO
(b) Joint pain	YES/NO	(g) Digestive problems	YES/NO
(c) Muscle weakness	YES/NO	(h) Headache	YES/NO

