- Previous history of muscular toxicity with a statin or fibrate
- Previous history of liver disease and/or where substantial quantities of alcohol are consumed
- In the elderly (age >70 years), the necessity of such measurement should be considered, according to the presence of other pre-disposing factors for rhabdomyolysis.
- Situations where an increase in plasma levels may occur, such as interactions (see section 4.5) and special populations including genetic subpopulations (see section 5.2)

In such situations, the risk of treatment should be considered in relation to possible benefit, and clinical monitoring is recommended.

If CK levels are significantly elevated (>5 times ULN) at baseline, treatment should not be started.

Creatine kinase measurement

Creatine kinase (CK) should not be measured following strenuous exercise or in the presence of any plausible alternative cause of CK increase as this makes value interpretation difficult. If CK levels are significantly elevated at baseline (>5 times ULN), levels should be remeasured within 5 to 7 days later to confirm the results.

Whilst on treatment

- Patients must be asked to promptly report muscle pain, cramps, or weakness especially if accompanied by malaise or fever.
- If such symptoms occur whilst a patient is receiving treatment with atorvastatin, their CK levels should be measured. If these levels are found to be significantly elevated (>5 times ULN), treatment should be stopped.
- If muscular symptoms are severe and cause daily discomfort, even if the CK levels are elevated to ≤ 5 x ULN, treatment discontinuation should be considered.
- If symptoms resolve and CK levels return to normal, then re-introduction of atorvastatin or introduction of an alternative statin may be considered at the lowest dose and with close monitoring.
- Atorvastatin must be discontinued if clinically significant elevation of CK levels (>10 x ULN) occur, or if rhabdomyolysis is diagnosed or suspected.

Concomitant treatment with other medicinal products

Risk of rhabdomyolysis is increased when atorvastatin is administered concomitantly with certain medicinal products that may increase the plasma concentration of atorvastatin such as potent inhibitors of CYP3A4 or transport proteins (e.g.

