- f) Participant decision regarding future statin use and the relationship to their primary outcome
- g) Whether patients found their own trial result helpful in making the decision about future statin use

TRIAL DESIGN: A pragmatic, randomised, double-blinded series of N of 1 trials recruiting 200 patients who have a clinical indication for statin treatment.

DIAGNOSIS AND INCLUSION / EXCLUSION CRITERIA:

Inclusion criteria:

- Adults (aged 16 and over)
- Registered in a participating GP practice
- Previously prescribed statin treatment in the last 3 years
- Stopped OR is considering stopping statin treatment due to muscle symptoms
- Provided fully informed consent.

Exclusion criteria:

- Any previously documented serum alanine aminotransferase (ALT) levels at or above three times the upper limit of normal
- Have persistent, generalised, unexplained muscle pain (whether associated or not with statin use) and have creatinine kinase (CK) levels greater than 5 times the upper limit of normal
- Any contraindications listed in the Summary of Product Characteristics for Atorvastatin 20 mg (Appendix 3)
- Should not participate in the trial in the opinion of the general practitioner.

TEST PRODUCT, REFERENCE THERAPY, DOSE AND MODE OF ADMINISTRATION: Once daily oral atorvastatin 20mg or placebo for 12 months.

SETTING: This trial is coordinated from the Clinical Trials Unit at London School of Hygiene & Tropical Medicine and conducted in patients registered in General Practice in England and Wales.

DURATION OF TREATMENT AND PARTICIPATION: Eligible patients should be randomised as soon as possible after the screening visit. Treatment period is for 12 months with a final follow-up within 3 month of end of treatment period.

CRITERIA FOR EVALUATION: Patients who enter data on muscle symptoms at least once during a treatment period with the IMP and at least once during a treatment period with placebo), irrespective of adherence to allocated treatment.

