1.4 ELIGIBILITY

Inclusion criteria:

- Adults (aged 16 and over)
- Registered in a participating GP practice
- Previously prescribed statin treatment in the last 3 years
- Stopped OR is considering stopping statin treatment due to muscle symptoms
- Provided fully informed consent

Exclusion criteria:

- Any previously documented serum creatine kinase (CK) levels at or above three times the upper limit of normal;
- Taken statins in the previous week and has an increase in serum alanine aminotransferase (ALT) at or above three times the upper limit of normal;
- Any contraindications listed in the Summary of Product Characteristics for Atorvastatin 20 mg (Appendix 3)

- Should not participate in the trial in the opinion of the general practitioner.

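### Protocol 2.7 excludes a raised CK only together with persistent generalised pain, so CK above 5 times ULN without such pain passes, against SmPC 4.4; SAP 1.4 states a third, conflicting rule

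*Protocol*

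**What the plan says.** Four places state the same joint rule. Protocol 2.7 excludes patients who have a certain kind of "muscle pain (whether associated or not with statin use) and have creatinine kinase (CK) levels greater than 5 times the upper limit of normal"; the pain must be lasting, widespread and without a known cause. The Protocol synopsis repeats this. Item 15 of the baseline form (Protocol Appendix 2) asks "Does the patient have persistent, generalised, unexplained muscle pain" and the CK condition in one yes/no question, with a test date that "must be within 3 months of visit" and a field for the result. SAP 1.1 joins the same pain condition to the same threshold: "and have creatinine kinase (CK) levels greater than 5 times the upper limit of normal".

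Three other places differ.

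- SAP 1.4 excludes "Any previously documented serum creatine kinase (CK) levels at or above three times the upper limit of normal", with no pain condition and no time limit. Its ALT bullet applies only to patients who took a statin in the previous week, whereas the ALT bullet in Protocol 2.7 covers any past result.
- SmPC 4.4 (Protocol Appendix 8) says: "If CK levels are significantly elevated (>5 times ULN) at baseline, treatment should not be started". It attaches no pain condition.
- Protocol 2.2 describes participants as people "who have experienced muscle symptoms while on statins but no substantial rises in CK or ALT".

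Protocol 2.7 also excludes anyone with an SmPC contraindication and anyone the GP thinks should not take part. Item 13 asks whether, in the GP's opinion, atorvastatin 20 mg daily can be started or continued.

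**The concern.** The word joining the two halves of the CK criterion narrows it. A patient with screening CK above 5 times ULN whose pain is absent, local, intermittent or explained does not meet both halves. Item 15 is then answered NO, and the form treats the patient as acceptable on CK. This is a patient in whom the trial's own reference document says not to start the drug. The exclusion for contraindications does not close the gap, because SmPC 4.3 lists hypersensitivity, liver disease or raised transaminases, and pregnancy-related conditions, but nothing on CK. The CK advice is among the warnings in 4.4.

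The same wording is used again during treatment. Protocol 2.10.4 asks the GP to confirm that a patient with intolerable symptoms still meets the eligibility criteria before continuing. Severe but local pain with CK above 5 times ULN would not fail 2.7, although SmPC 4.4 says treatment should be stopped at that CK.

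Separately, the SAP contradicts itself. Sections 1.1 and 1.4 cannot both describe who was eligible. SAP 2.3.8, which lists changes from the protocol, does not mention eligibility, so a reader cannot tell which rule was applied.

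**Working it through.** **Comparison of the rules.** The plan gives no figure for this point, so the first check is logical. Take four kinds of patient and read each text literally.

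| Patient | Protocol 2.7, synopsis, item 15, SAP 1.1 | SAP 1.4 | SmPC 4.4 |
|---|---|---|---|
| CK above 5 times ULN at screening, with lasting, widespread, unexplained pain | excluded | excluded | do not start |
| CK above 5 times ULN at screening, without such pain | not excluded | excluded | do not start |
| CK 3 to 5 times ULN at screening | not excluded | excluded | below the do-not-start threshold |
| Past CK above 5 times ULN on a statin, normal now | not excluded | excluded | re-introduction possible, with conditions |

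The second row is the defect: 2.7 admits a patient whom the SmPC says not to treat. In the third and fourth rows 2.7 does not contradict the SmPC on whether treatment may be given; SAP 1.4 is simply stricter. For ALT the order reverses. A past ALT at or above 3 times ULN in someone who has taken no statin in the last week is excluded by 2.7 but not by SAP 1.4.

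**How many patients.** The documents give no CK distribution for this population. SmPC 4.8 reports CK above 3 times ULN in 2.5% and above 10 times ULN in 0.4% of patients on atorvastatin, so the share above 5 times lies between these. Applying them to 200 participants is an assumption:

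- expected number: 0.004 × 200 = 0.8 to 0.025 × 200 = 5
- chance of at least one: 1 − 0.996^200 = 0.551 to 1 − 0.975^200 = 0.994

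These figures overstate the problem in so far as many participants will be off statins at screening, those with the specified pain are already excluded, and some would be stopped by the GP. They understate it if people selected for muscle symptoms have raised CK more often. An assumed 10% would give 0.10 × 200 = 20.

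**Effect on the primary estimate.** Each patient is compared with himself or herself under randomised order, so admitting these patients does not bias the comparison. It only changes the mix over which the effect is averaged. If they had a true statin effect of 20 to 40 mm and everyone else had none (assumed), the mean would move by share × effect:

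- 0.004 × 20 = 0.08 mm to 0.025 × 40 = 1.0 mm
- at the assumed 10%: 0.10 × 20 = 2 mm to 0.10 × 40 = 4 mm

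The target difference in Protocol 2.3 is 10 mm. The 10% case needs four times the highest SmPC rate (10 / 2.5 = 4), with every such patient passing the GP.

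**Cost in recruitment.** Protocol 2.3 expects 15% uptake: 200 / 0.15 = 1,333, which agrees with its figure of about 1,300 invitations. Replacing 0.8 to 5 patients needs 0.8 / 0.15 = 5.3 to 5 / 0.15 = 33.3 more.

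**The case against.** The strongest defence is that a GP stands between the wording and the patient. For patients found by record search, the GP confirms clinical eligibility before any invitation is sent (Protocol 2.6). Item 13 makes the patient ineligible if the GP would not start or continue atorvastatin 20 mg. The CK result is on the same form, and the SmPC is appended. After randomisation, 2.10.4 allows alternate-day dosing or stopping for the period, and 2.10.5 lets the GP withdraw a patient for any SmPC reason to stop. All of this stands, and it makes actual harm unlikely. It does not repair the criterion. Neither 2.7 nor item 13 gives the GP a CK threshold, item 15 signals that this CK is acceptable, and 2.10.5 permits withdrawal without requiring it.

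It is also fair to say that SAP 1.4 does not decide who is analysed. SAP 1.10 bases inclusion on having outcome data under both treatments. The conflict is therefore one of description.

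A reader might infer more than the documents support, in three ways.

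- *That any past CK rise should be a permanent bar.* SmPC 4.4 says that once symptoms have resolved and CK is normal, re-introduction "may be considered at the lowest dose and with close monitoring". A lifetime exclusion would be stricter than the SmPC. The fixed 20 mg dose is above the usual 10 mg start in SmPC 4.2, which is a matter for the GP at item 13.
- *That patients admitted through this gap cannot be identified later.* The screening CK is recorded at item 15, so they can be. Only older CK history is missing from the form.
- *That the trial would be re-challenging documented statin myopathy.* Protocol 2.2 uses that term for pain accompanied by CK or ALT rises. A pain-free CK rise does not meet it.

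**Conclusion.** The CK criterion is wrong as written, in one specific respect: it makes pain a condition for excluding a screening CK above 5 times ULN, and the appended SmPC does not. SAP 1.4 adds a rule that conflicts with SAP 1.1 and with the protocol on both CK and ALT.

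The size is small. About 0.8 to 5 of 200 patients would be affected if general on-atorvastatin rates held here and no GP intervened. At those rates the primary estimate would move by 0.08 to 1.0 mm even under the large assumed effects, so the consequence for the main result is likely to be negligible. The reasons to act are participant safety and a single, consistent eligibility rule.

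The sentence in Protocol 2.2 about no substantial CK rises is a background remark with no numerical definition, not an eligibility rule. It is still not guaranteed by 2.7, which admits patients with a past rise, and should be corrected.

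**What to change.** 1. In the synopsis, Protocol 2.7, item 15 and SAP 1.1, exclude CK above 5 times ULN at screening, with or without muscle pain. The repeat test after 5 to 7 days that SmPC 4.4 advises can serve as confirmation. Word the criterion so that it also works when eligibility is re-confirmed under 2.10.4.
2. Replace the CK and ALT bullets of SAP 1.4 with the corrected text of Protocol 2.7.
3. Do not exclude patients whose past CK rise has returned to normal. Add one field to the baseline form for the highest past CK on a statin, so that they can be described.
4. Correct the sentence in Protocol 2.2 so that it no longer says participants had no substantial CK rises.

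The cost is one form field, text edits, and the loss of very few patients: roughly 5 to 33 extra invitations under the assumptions above. The design, sample size and analysis model do not change.

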2.8 RANDOMISATION

Patients eligible for inclusion will be randomised by the Research Nurse/GP practice trial team using the online London School of Hygiene & Tropical Medicine (LSHTM) CTU randomisation system to a sequence of blinded placebo and atorvastatin treatment periods. There are six paired (statin-placebo or placebo-statin) treatment periods each of two months' duration. In practice, this means that each individual is randomised (with equal probability) to one of the following eight sequences (with P=placebo, S=statin):

	Treatment Period					
	1	2	3	4	5	6
Sequence 1	S	P	S	P	S	P
Sequence 2	S	P	S	P	P	S
Sequence 3	S	P	P	S	S	P
Sequence 4	S	P	P	S	P	S
Sequence 5	P	S	S	P	S	P
Sequence 6	P	S	S	P	P	S
Sequence 7	P	S	P	S	S	P
Sequence 8	P	S	P	S	P	S

Randomisation codes will be generated and secured by the Information Technology team at LSHTM CTU, who has procedures to ensure the trial team remains blinded. The codes will be made available to a Good Manufacturing Practice (GMP) certified clinical trial supply company explicitly for the treatment packs to be created in accordance with the randomisation list.

2.9 TREATMENT

The trial treatment consists of once-daily oral administration of Atorvastatin (20mg) capsules, which will be compared with matching placebo (Microcrystalline Cellulose). The treatment phase of the trial will be one year in duration for each patient. A blinded placebo, identical in size, colour, smell and packaging to the active statin, has been chosen to prevent knowledge of treatment from affecting symptom scores.

Two months' supply of allocated treatment will be posted to the patient every 2 months. Treatment should start within 4 weeks of randomisation. Patients who have not started by the 3rd week post randomisation will be contacted by the CTU. Such patients will therefore have a longer study period.

2.9.1 DOSE SELECTION

Atorvastatin is recommended by the current NICE guidelines for lipid modification;² 20mg is the recommended dose for primary prevention of cardiovascular disease. Atorvastatin is also recommended by NICE for secondary prevention² and for patients with a high risk of adverse events (our patient population), a dose lower than 80mg is recommended. The most commonly used dose is 20mg. A visually matched placebo has been chosen as an appropriate comparator for two reasons. Firstly, patient expectation of symptoms while on statins is likely to affect their experience of symptoms. A placebo control should minimise bias arising from knowledge of allocation. Secondly, withholding statin treatment from patients during placebo treatment periods is justified because the trial will recruit patients who have recently stopped using statins (and therefore are not currently receiving any benefit from statins) and those who wish to discontinue. If patients in the trial tolerate the active treatment periods with few symptoms, then this trial is likely to increase their usage of statins in the long term.

2.9.2 DRUG MANUFACTURE, BLINDING AND SUPPLY OF TRIAL MEDICATION

The active trial drug atorvastatin (as atorvastatin calcium trihydrate) will be purchased on the open market. Atorvastatin is manufactured by Sharp Clinical Services (UK) Ltd under Marketing Authorisation Number 10284. The Marketing Authorisation guarantees that the product has been manufactured and released in accordance with the United Kingdom's Good Manufacturing Regulations.

Placebo will be manufactured specially to match the atorvastatin by a GMP certified manufacturer. Capsules and packaging will be identical in appearance for both active treatment and placebo. DBCaps® capsules which has a unique locking mechanism to help with assuring the integrity of the blind will be used for over encapsulation of both active and placebo treatments. Additionally, patients will be asked to swallow the capsule whole without chewing or breaking it. The blinding process and first stage Qualified Person (QP) release will be done by the designated clinical trial supply company. The blinding process will involve encapsulating the active tablet, complete removal of the original manufacturer's label and replacement with the clinical trial label bearing the randomisation number which will be used as the pack identification. Other pack label text will be identical for both atorvastatin and placebo treatments and will be in compliance with requirements for investigational medicinal products.

The designated clinical trial supply company will also be responsible for maintaining the Product Specification File (PSF) until final database lock and unblinding of the trial data. The CTU will be

responsible for assuring all relevant approvals are available and that the patient is eligible for the trial before release of the trial medication to a patient. A separate Manual of Operating Procedures (MOP) will detail the drug accountability system. The MOP will also detail labelling of the trial treatment and other processes for assuring adherence to Good Manufacturing Practice.

2.9.3 ADMINISTRATION OF TRIAL MEDICATION

Patients will receive their allocated trial medications through the post and they will be asked to take the study medication daily through the six two-month treatment periods. Ideally there should be no break between treatment periods. However, if for any reason there is a break, patients can simply restart taking the trial medication as soon as possible.

Patients will be asked to take one capsule orally once daily at a time of day convenient to them. Capsules should be swallowed whole. Patients will be given written instructions on how to take the study medication. At the start of each two-month treatment period, patients will be asked to inform the trial team about their first date of study medication use using the trial's mobile application (app), email, text message, Freephone telephone service or a pre-paid postage reply slip - whichever is easier to ensure data collection occurs on the correct days. A Freephone telephone number will be provided for patients to call if they have any questions. Adherence to the study medication will be collected on the same days as other data as part of the outcome data collection.

